Procedures: Procedures are identical to Study Visit 3. However, we will also include the following two neuropsychological exams, which were included at the Informed Consent and Screening Visit (Visit 1) rather than the Baseline MRI Visit (Visit 3).

Visuospatial Attention: Trail-Making Test A and B121 (baseline testing to take place during screening visit; approx. duration: 5 min)

Executive Functions: Stroop test, Victoria version121 (baseline testing during screening visit)

Procedures for Re-Screening:

Any participant who was determined eligible over three months before the exercise training program start date will need to be rescreened. The proposed timeline for eligibility and re-screening is as follows:

Eligibility timeline:

Eligibility determined at or less than 3 months before projected training start date: valid. Eligibility determined over 3 months but at or less than 12 months before projected training start date: requires phone re-screening, that will be valid for the following 3 months, detailed below.

Eligibility determined more than 12 months before projected training start date: requires a full visit Study Visit 1b (Procedures are identical to Study Visit 1) to re-assess eligibility, the will be valid for the following year.

The re-screening protocol will include a phone re-screening that consists of direct questions regarding all of the inclusion/exclusion criteria that are subject to change within 12 months or less (see attached Phone Re-Screening protocol).

After re-screening, the principal investigator and study staff member will discuss the participant's responses, and the investigator will determine whether or not the participant is still eligible for participation.

Inclusion/exclusion criteria that will NOT be directly re-screened include the following:

1. Fluent in English (must have attended elementary school and higher in English) (Inclusion Criterion #4): this cannot change from the time of initial screening to re-screening.

2. Dementia Rating Scale performance (Exclusion Criterion #4): we do not expect the participant's score to change by more than one point within the proposed 3-12-month timeline for re-screening. However, participants who originally scored a 9 on the AMSS or AEMSS at their Visit 1 will be required to come in for a full re-screening (Visit 1b) to confirm that cognitive decline has not occurred since Visit 1.

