3. Impaired participant performance on the Trail Making Test or Stroop Test (Exclusio n Criterion #5): this will not be re-assessed. Other re-screening questions will be used to inform the study staff of any changes to brain structure/function (i.e., any recent diagnoses regarding neurological/psychological/psychiatric conditions). If the investigator is concerned that the participant may not perform at normative levels on neuropsychological testing, the participant will be invited in for a full re-screening (Visit 1b).

4. Grip strength test performance (Exclusion Criterion #6): this will not be re-assessed. Other rescreening questions will be used to inform the study staff of any changes to brain structure/function (i.e., any recent diagnoses regarding neurological/psychological

/psychiatric conditions) or musculoskeletal health (i.e., any recent diagnoses of musculoskeletal impairments).

Additionally, the obesity criterion (Exclusion Criterion #8) will be assessed based on the anthropometric measure obtained from the participant in his or her initial Visit 1:

a. Participants with BMI < 30: for a participant, whose BMI is below 30, we will ask during the rescreening if he or she has gained weight since the initial study visit. If the answer is yes, the previously measured height of the participant and the self-reported current weight of the participant will be used to calculate BMI. If the participant still falls below a BMI of 35 with his or her new weight, then he or she will still be considered eligible for the study. If the participant falls at or above a BMI of 35, he or she will be invited in for a full re-screening (Visit 1b). This is due to the fact that a BMI of 35 or greater is one of the exclusion criteria to be considered in the obesity criterion (exclusion criterion#8).

b. Participants with $BMI \ge 30$: these participants will be invited in for a full re-screening (Visit 1b).

Procedures for Pilot studies:

For pilot studies involving only fMRI and/or cognitive testing (no neuropsychological assessment, fitness testing, or exercise training), participants will already come in for their initial study visit tentatively scheduled for behavioral testing and/or fMRI on the same day and/or on a day in the near future. However, the study staff will confirm the visit based on 1) whether they are still interested after explanation of the procedures and 2) whether they are eligible to participate based on screening.

Cognitive pilot:

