Measurements: upper body strength in lbs or kg (based on chest press and latissimus dorsi pulldown), lower body strength in lbs or kg (based on leg press)

3) Increased lean body mass

Measurements: Percent lean body mass from BIA (and/or skinfold measures)

4) Neuropsychological test performance: improved performance scores on tests of spatial cognition, verbal memory, visuo-spatial memory, visuo-spatial attention, and executive functions post-exercise training compared to baseline and compared to controls

Measurements: neuropsychological test scores

Data Analysis

Provide a description of your plan for data analysis. State the types of comparisons you plan (e.g. comparison of means, comparison of proportions, regressions, analysis of variance). Which is the PRIMARY comparison/analysis? How will the analyses proposed relate to the primary purposes of your study? If you are doing qualitative research please state how comparisons will be made.

Specific Aim #1:

Behavioral and Fitness Data Analysis. The primary measures for the primary cognitive task (Sternberg memory load task) are % correct and reaction times, and for fitness are estimated VO 2 max. The primary statistical analyses will be repeated-measures ANOVAs with the factors group (aerobic vs. control) and time (pre vs. post) to examine group x time interactions on the outcome measures. Posthoc tests (e.g. Tukey tests) will examine if a significant group x time interaction is due to a greater improvement post-intervention in the aerobic exercise group compared to controls. Dependent measures will be tested for normality and skewed data log-transformed. We will use an alpha of 0.05, corrected for multiple comparisons.

Univariate fMRI and Functional Connectivity Analyses. We will use SPM8 and related software for statistical analysis of fMRI data. We will estimate voxel-based Statistical Parametric Maps (SPMs)

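### Trail-Making and Stroop take their baseline at screening, and phone re-screening does not repeat them, so their pre-post interval can reach about 15 months instead of about 4

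*Combined protocol and SAP*

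**What the plan says.** The section on Study Visit 41 adds Trail-Making A and B and the Victoria Stroop to the follow-up battery. For Trail-Making it notes "baseline testing to take place during screening visit", and it says the same for Stroop. The other cognitive outcomes are first measured at Visit 2 (the Mnemonic Similarity Task) or Visit 3 (the scanner tasks and the post-scan battery).

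Procedures for Re-Screening sets three tiers by the age of the eligibility decision at the projected start of training:

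- Up to 3 months: still valid.
- The middle tier: "Eligibility determined over 3 months but at or less than 12 months before projected training start date: requires phone re-screening".
- Beyond 12 months: "requires a full visit Study Visit 1b (Procedures are identical to Study Visit 1) to re-assess eligibility".

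For performance on Trail-Making and Stroop at phone renewal, the same section states "this will not be re-assessed. Other re-screening questions will be used to inform the study staff of any changes to brain structure/function".

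Some participants in the middle tier are sent to Visit 1b instead: those with a BMI of 30 or more, a recalculated BMI of 35 or more, a Dementia Rating Scale score of 9 (AMSS or AEMSS), or a concern by the investigator about neuropsychological performance.

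Under Outcomes, visuo-spatial attention and executive functions belong to the fourth secondary outcome, which is improvement "post-exercise training compared to baseline and compared to controls". Data Analysis applies a repeated-measures ANOVA with the factors group and time, and time has only the levels pre and post.

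**The concern.** A pre-training score should describe the participant shortly before training. For these two tests it describes the participant at screening, which under phone renewal may be up to a year earlier. The planned ANOVA treats such a participant like one tested three weeks before training, because no term for elapsed time is named.

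The delay is foreseeable. The protocol has a tiered re-screening timeline, mentions a waiting list, and forms training groups of about 3 to 6 people around shared availability. It also accepts that cognition may change in this window, since a Dementia Rating Scale score of 9 requires a return visit to rule out decline. It offers a stability argument for that scale but none for Trail-Making or Stroop.

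The same Visit 1 scores also serve as an exclusion filter (Exclusion Criterion #5). Removing low scorers on the measure that then becomes the pre score invites regression to the mean in within-arm change.

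At stake are the interpretation of within-arm change on two secondary measures and some precision in the between-arm comparison.

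**Working it through.** **Inputs from the documents**

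- Visits 1 to 3: up to about 3 weeks (Study Summary).
- Training: 12 weeks (Study Summary).
- Total participation: about 4 months (Study Summary).
- Oldest Visit 1 that phone renewal accepts: 12 months before the projected training start (Procedures for Re-Screening).
- Planned size: 21 per group (Sample Size Justification).

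**Assumptions**

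- End of training to Visit 41: 0 to 4 weeks (not stated).
- Pre-post correlation r: 0.7 at the nominal interval, 0.6 or 0.5 at the long interval. The documents give no correlation.
- Share of participants affected: 10% or 25%. The documents give no number.

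**Step 1. Reproduce the plan's own duration.** With 4.348 weeks per month, (3 + 12 + 0)/4.348 = 3.4 months and (3 + 12 + 4)/4.348 = 4.4 months. With 2 to 3 weeks to Visit 41 the result is 3.9 to 4.1 months, which agrees with the stated 4 months.

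**Step 2. Longest interval without re-screening.** 3 + 12/4.348 = 5.8 months. With 4 weeks to Visit 41, 3 + 16/4.348 = 6.7 months.

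**Step 3. Longest interval on the phone route.** 12 + 12/4.348 = 14.8 months. With 4 weeks to Visit 41, 12 + 16/4.348 = 15.7 months. Hence about 15 months.

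**Step 4. Effect on the variance of change.** With equal SDs before and after, Var(change) = 2(1 − r) in SD² units.

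| r | Var(change) | Increase over r = 0.7 |
|---|---|---|
| 0.7 | 0.6 | – |
| 0.6 | 0.8 | 0.8/0.6 − 1 = 33% |
| 0.5 | 1.0 | 1.0/0.6 − 1 = 67% |

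**Step 5. Effect at trial level.**

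- 25% affected: 0.75 × 0.6 + 0.25 × 0.8 = 0.65, up 8%. With 1.0 in place of 0.8 the result is 0.70, up 17%. The SD of change rises by a factor of √1.083 to √1.167, about 4% to 8%.
- 10% affected: 0.10 × 33% = 3% to 0.10 × 67% = 7% in variance.

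**Step 6. Side by side.** The Study Summary describes three initial visits within about three weeks, followed by training. Procedures for Re-Screening allows up to 12 months between Visit 1 and training on the phone route. These describe different timelines, and nothing sets a maximum gap from Visit 2 or 3 to the start of training.

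**The case against.** The strongest reply is that this trial is randomised with an active control arm, and that the outcome is judged against controls as well as against baseline. Ageing, an old baseline and selection on the screening score act alike in both arms on average. A reader might infer that the estimated exercise effect on these tests is biased. The documents do not support that: the group × time test is protected by randomisation, and what remains is noise and chance imbalance with 21 per arm.

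A reader might also take 15 months as typical. It is a maximum. Eligibility up to 3 months old needs no renewal, several routes lead to Visit 1b, where both tests are repeated, and the number renewed by phone only could be few or none. Nor is about 18 months well supported. A phone renewal is valid for 3 months, but the rule that more than 12 months requires Visit 1b argues against letting training start at month 15.

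Nor do the documents show that the problem is confined to these two tests. Only the summary places Visits 2 and 3 close to training.

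The size of the selection effect cannot be worked out, because the cut-off in Exclusion Criterion #5 is not in the available text. The correlations are assumed, and the two tests belong to one secondary outcome.

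All of this stands, and it limits the consequence. It does not remove the gap: phone renewal can leave these two measures with a baseline up to a year old at the start of training, and the analysis plan does not address it.

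**Conclusion.** The point holds as a minor design weakness. For participants renewed by phone, the pre-post interval for Trail-Making and Stroop can reach a ceiling of 14.8 to 15.7 months (assuming 0 to 4 weeks to Visit 41), against about 4 months nominally.

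The between-arm comparison loses some precision and is open to chance imbalance in the interval; it is not systematically biased. Within-arm change is harder to read, because it mixes training with elapsed time and with selection on the same score.

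The loss is a 33% to 67% rise in change variance among those affected, or about 8% to 17% overall if a quarter are affected. These figures depend wholly on the assumed correlations and share, so they illustrate the scale and are not the expected effect. The primary cognitive and imaging outcomes do not use these scores.

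A related gap is that the plan does not say whether the Visit 1 or the Visit 1b score is the baseline for participants who have both. If the Visit 1 score were kept, the interval could exceed 15 months. Visit 1b is itself valid for a year, so even its score can be about 15 months old by Visit 41.

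**What to change.** Give Trail-Making and Stroop to all participants at Visit 3, mirroring Visit 41. Name those scores as the analysis baseline, and keep Visit 1 and Visit 1b scores for eligibility only. This also settles which score counts after a Visit 1b and separates the baseline from the exclusion filter.

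Reconcile the three-week run of initial visits in the Study Summary with the 12-month window in Procedures for Re-Screening, so that Visit 3 falls close to the start of training. Without that, moving the tests to Visit 3 does not guarantee a recent baseline.

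The cost is about 10 to 15 minutes by the protocol's own timings (5 to 10 for Trail-Making, about 5 for Stroop) at a visit of about 4 hours. There is also one extra practice exposure. No alternate forms are named for these two tests, so practice effects are real, but the exposure comes before training and is equal in both arms.

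Retesting only those with an old Visit 1 would be cheaper but is not preferred, because it mixes first-exposure and second-exposure baselines.

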2. Body composition analysis using the InBody Test (approx. duration: less than 15 min) The InBody Test uses safe, low-level currents sent through the body via hand and foot electrodes. (The participant contacts these electrodes by standing on the device, which resembles a scale, and holding the cylindrical hand-held electrodes.) The impedance that the currents encounter are measured, and from there, body composition is derived. The amount of this current is slight enough that the participant cannot feel it. The InBody Test will provide an estimate of total body water, dry lean mass, body fat mass, weight, skeletal muscle mass, body mass index, and percent body fat. These estimates are printed out on the

InBody Results Sheet, which has been included with this protocol (InBody_E_Book.pdf). Each participant will be offered a copy of his or her results to compare body composition from before and after the exercise intervention. Outcome measures for the purposes of this study include weight, body mass index, and percent body fat.

3. Cardio-respiratory fitness tests (incremental work rate test) (approx. duration: 30-40 min) We will use standard submaximal clinical exercise testing procedures, including that of a submaximal, incremental work rate test, designed to ensure participant safety and measurement accuracy (Cooper and Storer, 2001; Thompson et al., 2010). We will follow the guidelines established by the American College of Sports Medicine for submaximal clinical exercise testing (ACSM; Thompson et al., 2010).

We will use a modified Balke treadmill protocol that uses a fixed walking speed and increasing increments in grade. We will choose the speeds and grades used for each participant (Cooper and Storer, 2001) so that all participants walk at a relatively comfortable pace with the grade increments calculated to provide a total test duration of 8-12 minutes (Buchfuhrer, 1983). The test will be continued until the participant reaches 85% of his or her age-predicted maximum heart rate (HRmax = 206.9 - (0.67 × age)) or 70% of heart rate reserve (HRreserve = HRmax –HRrest). While this test does not allow direct measurement of maximum oxygen uptake (VO2max),

the results of this test allow us to predict VO2max based on the known linear relationship between heart rate and VO2max. VO2max is a secondary outcome measure. Notably, participants will warm up for 3 to 4 minutes and cool down for 7 to 10 minutes before and after the test, respectively.

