they must not have missed more than 1 exercise session per week to receive the finishing bonus. In the case that a participant anticipates being unable to attend one or more of the exercise training sessions, the participant will have the opportunity to work out on his or her own if he or she informs the trainer ahead of time. The trainer will then provide the participant with "homework" and a training log. The homework will describe the exercise the participant should do while away. The participant will be reminded that he or she will need access to exercise training equipment. The trainer will instruct the participant in how to fill out the training log. We may ask the participant to wear a heart rate monitor or activity monitor or similar device during the exercise. We will provide this device to them. A study staff member may call them about their training progress while they are away. Participants will be expected to return the training log to the trainer after their return. Participants will not have the opportunity to receive homework during the first four weeks of the exercise training program. This is for the safety of the participants, given that the trainers will monitor their progress and instruct them in proper technique during the first four weeks. If a participant anticipates being unable to participate during this time, we may exclude him or her from participating in this study or place him or her on a waiting list. A participant will not necessarily be excluded if he or she is not available for the duration of the study, unless the participant anticipates that he or she will miss any of the study visits (study visits 1, 2, 3, 40, 41) and/or if he or she anticipates missing three exercise sessions in a row without fulfilling the homework and training log requirements. Make-up sessions during the same week will also be available.

Exercise diary/log. We will ask the participants to continue using the exercise diary/log until the study is completed. We will go over the exercise diary with the participant on approximately a weekly basis.

5) Study Visit 40: Follow-up fitness testing and body composition exam

Duration: Approx. 2-2.5 hours

Location: BU Fitness and Recreation Center

Procedures: Procedures are identical to Study Visit 2.

6) Study Visit 41: Follow-up MRI exam

Duration: Approx. 4 hours

Location: Cognitive Neuroimaging Center at Boston University Charles River Campus

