We will protect each participant's confidentiality by labeling identifiable information with a code and keeping the key to the code separately from the research data either in a password-protected computer or as a paper file in a locked file cabinet. The master code is limited to BUMC investigators and we will not release it to anyone outside the institution. [name] will have access to the names and birthdates of participants in addition to the research data. Information will be stored on secure servers using REDcap or similar software. If it is necessary to use a laptop's hard drive for storage of identifiable information this laptop's hard drive will be encrypted with Truecrypt or similar disk encryption software prior to storing this information. All research staff will receive training in human subject protection and the HIPAA rule.

Potential Benefits

Benefits to subjects

Participants may or may not benefit from taking part in this study. Possible benefits to subjects include improved cardiovascular health, physical fitness and/or strength, and weight loss from participating regularly in the exercise training program.

Benefits to society

Others may benefit in the future from the information that is learned in this study. These potential benefits may include improved brain function through exercise and knowledge about how exercise affects the brain and cognitive (thinking) processes.

Risk to Benefit Ratio

Assessment of Risk/Benefit Ratio

Even though the exercise interventions, exercise testing and MRI procedures performed are solely done to answer research questions, the risks are very reasonable in relation to anticipated benefits. This is so, because the risks associated with the research study are only minimal, while the anticipated benefits to subjects are expected to be more than minimal due to the well-known health-related benefits associated with regular exercise.

Selected References

- Altman, J., & Das, G. D. (1965). Autoradiographic and histological evidence of postnatal hippocampal neurogenesis in rats. *Journal of Comparative Neurology*, 124(3), 319–335. https://doi.org/10.1002/CNE.901240303

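### Secondary outcome 3 is named as a gain in lean body mass but measured as percent lean body mass, which can rise through fat loss with no lean gain

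*Combined protocol and SAP*

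**What the plan says.** Under Outcomes, Secondary outcomes for all aims, the third item is headed "3) Increased lean body mass". Its measurement line reads "Percent lean body mass from BIA (and/or skinfold measures"). The item states no group, no unit other than percent, and no contrast between arms.

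The procedure is in Study Visit 2, under "Body composition analysis using the InBody Test". The device is said to give an "estimate of total body water, dry lean mass, body fat mass, weight, skeletal muscle mass, body mass index, and percent body fat". The same paragraph then states: "Outcome measures for the purposes of this study include weight, body mass index, and percent body fat". Study Visit 40 repeats the measurement: "Procedures are identical to Study Visit 2". Neither visit describes skinfolds. The body measurements at the screening visit are weight, height, and waist and hip circumference.

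Under Potential Benefits, the possible gains for participants are "improved cardiovascular health, physical fitness and/or strength, and weight loss from participating regularly in the exercise training program".

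**The concern.** The outcome's name asks whether participants gained lean tissue. The measure is a ratio with total weight, including fat, in its denominator, so it also moves when only fat changes. The protocol lists weight loss as a possible result of training, so this is not a remote case. An analyst who follows the measurement line as written could find an increase in the outcome when lean mass has not changed.

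There are two smaller problems. The body-composition outcomes listed at Visit 2 (weight, BMI, percent body fat) do not appear among the secondary outcomes, and the Visit 2 list names no lean-mass outcome. The measurement line also allows a second method, joined by and/or, with no procedure and no rule for choosing between the methods.

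**Working it through.** The plan gives no figure to reproduce for this outcome. The check uses the definition of the measure and assumed body compositions, because the documents give no baseline weights, fat percentages or expected changes.

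**Formula.** Let L be lean mass and F fat mass, with weight = L + F. Then

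percent lean = 100 × L / (L + F) = 100 − percent fat.

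**Base case (assumed).** Weight 80 kg, F = 30 kg, L = 50 kg. Percent lean = 50/80 = 62.5%.

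| Change from baseline | Calculation | Percent lean | True change in L |
|---|---|---|---|
| Lose 2 kg fat | 50/78 | 64.1% (+1.6 points) | 0 kg |
| Lose 3 kg fat | 50/77 | 64.9% (+2.4 points) | 0 kg |
| Lose 3 kg fat and 1 kg lean | 49/76 | 64.5% (+2.0 points) | −1 kg |
| Gain 2 kg lean, fat unchanged | 52/82 | 63.4% (+0.9 points) | +2 kg |
| Gain 1 kg fat and 1 kg lean | 51/82 | 62.2% (−0.3 points) | +1 kg |

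The third and fifth rows show that the measure can move in the opposite direction to lean mass. The first and fourth show that losing 2 kg of fat raises it more than gaining 2 kg of lean tissue does.

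**How much lean loss can be hidden.** If fat falls by f, percent lean does not fall unless the lean loss exceeds f × L/F. With f = 3 kg this is 3 × 50/30 = 5 kg (check: 45/72 = 62.5%, the baseline value).

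**Range.** With weight 70 to 90 kg, fat 30% to 40%, fat loss 1 to 3 kg and lean mass constant:

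- Smallest rise (90 kg, 40% fat, 1 kg lost): 54/89 = 60.67%, against 60%, or +0.67 points.
- Largest rise (70 kg, 30% fat, 3 kg lost): 49/67 = 73.13%, against 70%, or +3.13 points.

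**With the measure in kg.** Lean mass = weight − body fat mass. In the base case, 80 − 30 = 50 kg before. After losing 2 kg of fat it is 78 − 28 = 50 kg, a change of 0 kg, as it should be. Weight and body fat mass are both on the device's list of estimates and are obtained at both visits.

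**The case against.** The strongest reply is that no information is lost. Weight is a named outcome at Visit 2 and is measured again at Visit 40, so lean mass can be recovered as weight × percent lean: 80 × 62.5% and 78 × 64.1% both give 50 kg. The measurement line also says openly that the quantity is a percentage, and renaming the outcome percent lean mass would remove the mismatch without a new measure. All of this stands. It shows that the repair is easy, but the outcome as written still pairs a lean-mass name with a measure that does not isolate lean mass.

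A reader might infer three stronger claims that the documents do not support.

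- **That the two outcome lists contradict each other.** The Visit 2 sentence uses *include*, so its list need not be complete. Percent lean is also the complement of percent body fat, which is on that list. The lists are unaligned, not in conflict.
- **That fat loss will be reported as lean gain.** Weight loss is given only as a possible benefit, no diet intervention is described, and weight and percent fat are also outcomes. The error is possible, not certain.
- **That the comparison of aerobic with strength training would be masked or reversed.** Outcome 3 states no direction between arms, unlike outcomes 1, 2 and 4. The analysis section does not mention body composition, and the documents give no expected change in fat or lean mass in either arm.

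**Conclusion.** The point holds as a mismatch between the outcome's name and its measure. Percent lean body mass can increase with no lean gain, and even with lean loss. In the assumed base case the apparent rise is 1.6 to 2.4 points with 0 kg of lean change; over the wider assumed range it is 0.67 to 3.13 points. These sizes depend on assumed body compositions and fat losses and on treating all non-fat mass as lean. The direction of the problem follows from the formula alone.

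The consequence is limited. This is one of four secondary outcomes, and it bears on neither the primary analysis nor the sample size.

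**What to change.** 1. Define secondary outcome 3 as the change in lean body mass in kg from Visit 2 to Visit 40, calculated as weight minus body fat mass from the InBody output. State this one quantity: dry lean mass and skeletal muscle mass are listed as separate device outputs and should not be left as alternatives.
2. Report percent body fat separately, under its own name.
3. Align the outcome list under Study Visit 2 with the secondary outcomes, so that both name the same body-composition measures, including lean mass.
4. Remove the skinfold option.

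The cost is wording and one subtraction per visit. No new measurement is needed, since both inputs are already collected at both visits. The change should be made before the outcome data are analysed, so that the measure is not chosen after the results are seen.
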